3.1. Study Design Overview

This is an adaptive, open label phase I dose escalation study of the safety, tolerability, immunogenicity and intra-dermal administration dose finding for the pEVAC-PS vaccine candidate against SARS-CoV and SARS-CoV-2. This study will recruit up to 36 healthy volunteers in up to 3 stages. All volunteers recruited will be healthy, male or non-pregnant female adults aged between 18 and 50 years who have been vaccinated no less than 12 weeks prior with 2 doses of a SARS-CoV-2 vaccine and have no history of infection and are seronegative for N.

The sentinel participant in each group will be observed for 1hr post vaccination and contacted 24hrs afterwards by the medical team to review symptoms and check against symptom diary. If no safety concerns are identified (section 7.9.1), the subsequent 5 participants can be vaccinated a minimum of 1 hour apart. Each participant will be observed for 60 minutes post vaccination. After review of participants in group 2a at 72hrs post dosing with the second immunisation, if no stopping criteria have been met (section 7.9) then the sentinel participant at the next dose level in 2b can be vaccinated.

Figure 1 (page 19) shows our approach to dose escalation to maximise participant numbers in groups that may inform future large scale clinical trials.

Stage 1

Group 1 will consist of 6 volunteers receiving 2 administrations of the lowest dose of ID injection at 0.2mg. There will be a review of the immunogenicity data 4 weeks following the second administration prior to proceeding to stage 2.

Stage 2

Group and dose allocation in stage 2 will depend on the results of the safety and immunogenicity analysis in stage 1, according to pre specified target immunogenicity outcomes.

a) Primary immunogenicity target met

Group 1 will be expanded with an additional 12 participants receiving 2 administrations of 0.2mg ID. If no safety issues are noted during expansion group and immunogenicity targets continue to be met, the study will be halted and a further review will be conducted by the study team to determine a reduced dose formulation and study regime, which will follow as a planned amendment to this protocol.

b) Primary immunogenicity target not met

2 additional groups consisting of 9 participants will be enrolled. Group 2a will receive 2 administrations of 0.4mg ID, and group 2b will receive 2 administrations of 0.8mg ID.

c) Very Poor/ No response

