3.1.1. Immunogenicity endpoints

The adaptive protocol is based on reviews of immunogenicity data which will be made 4 weeks following the second administration of pEVAC-PS (8 weeks following the first dose). The decision for how to proceed will be made on the basis of the proportion of participants within each group who have seroconverted. Seroconversion will be defined as a positive readout from the SARS-CoV and/or SARS-CoV-2 RBD ELISA. The dose used for each group will be classified as either having met immunogenicity target, failed to meet immunogenicity target, or had very poor / no response. Proportions of participant seroconversion will be classed as the following:

Stage 1 – Meets immunogenicity target if 5 or 6 out of 6 participants have at least a 2-fold increase in Ab titre (at 0.2mg) we proceed to Expanded Group 1.

- Stage 2 (Expanded Group 1) if 12/12 participants have a 2-fold increase in Ab titre (at 0.2mg) consider to re-formulate and reduce the dose for a new study.
- Stage 2 (Expanded Group 1) if 10 or more of the 12 participants have at least a 2-fold increase in Ab titre (at 0.2mg) we select 0.2mg as the optimum dose to move forward into a Phase II study.
- Stage 2 (Expanded Group 1) if <=9 participants have a 2-fold increase in Ab titre (at 0.2mg) then a further 9 participants will be recruited to group 2a (0.4) and 2b (0.8mg) each, to be run in parallel.

 - The study will conclude after running groups 2a and 2b.

Stage 1 – Fails to meet immunogenicity target if only 3 or 4 out of 6 participants have at least a 2-fold increase in Ab titre, then we proceed to Groups 2a (0.4mg) and 2b (0.8mg) in parallel.

- Stage 2 if 7-9 or more participants have a 2-fold increase in Ab titre (at 0.4 or 0.8 mg) we expand whichever group has the higher number of responders. If both groups 2a and 2b have 9 responders, we will expand the lower dose.
- Stage 2 if <7 participants have a 2-fold increase in Ab titre (at 0.4 or 0.8 mg) we move to Stage 3 and increase dose to 1.2mg.

Stage 1 – With a poor response, if 2 or less participants out of 6 have a 2-fold increase in Ab titre, we proceed to Groups 2a (0.8mg) and 2b (1.2mg) in parallel.

- Stage 2 if 7-9 participants have a 2-fold increase in Ab titre (at 0.8 or 1.2mg) we expand whichever group has the higher number of responders.
- Stage 2 if <7 participants have a 2-fold increase in Ab titre at 0.8mg and 1.2mg the trial will conclude.

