3.5. Dose escalation

The sentinel participant in each group will be observed for 1 hr post vaccination for any local reactions and contacted 24hrs afterwards by the medical team to review symptoms and check against symptom diary. If no safety concerns are identified (section 7.9.1), the subsequent 5 participants can be vaccinated a minimum of 1 hour apart. Each participant will be observed for 60 minutes post vaccination. After review of participants at 72hrs post dosing, if no stopping criteria have been met (section 7.9) then the procedure can be repeated with the first subject at the next dose level.

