5.5 Participant visits

5.5.1 Vaccination Visits

Following review of safety blood results and GP medical history, eligible subjects will be booked to attend a vaccination visit on Day 0. After re-checking inclusion and exclusion criteria, an abbreviated physical examination (at the investigator's discretion) and measurement of physical observations, subjects will be enrolled into a study group for vaccination. Volunteers will be enrolled into each group or subgroup sequentially. Volunteers will be informed of which group they will be enrolled into. Volunteers will not be randomised into a group in this study.

If medical status and/or physical examination suggest significant changes have occurred since screening, the Day 0 visit can be re-scheduled, or the subject excluded from the study if he/she fails to meet the inclusion and exclusion criteria. The study team will advise the volunteer prior to the dosing visit that receipt of licensed vaccines e.g. (FLU vaccine) is not permitted within the month preceding vaccination or the month following each vaccination. Should a volunteer have received a licensed vaccine in the month prior to pEVAC-PS vaccination the Day 0 visit will be rescheduled to an acceptable time-point.

Before vaccination, the investigator must check for any symptoms of an acute illness or body temperature \geq 37.5°C. In such a situation, the subject may be vaccinated at a later date within the screening window or be withdrawn at the discretion of the investigator. The vaccine will be administered as detailed in **Section 6.3** *Dosage and administration of study vaccine'*.

Following vaccine administration, subjects will be observed for a minimum of 60 minutes for the development of any acute reactions, or longer if deemed necessary.

Subjects will be provided with a subject diary, thermometer, and ruler to measure and record body temperature, solicited local and systemic AEs.

This will be repeated on Day 28 for administration of the second dose of vaccine.

If the volunteer has remained well during this observation period, they may go home and will receive a follow up telephone call the next day.

Any significant safety concerns that have arisen during the observation period will be communicated to the CI and local safety monitor. An extended period of observation will be instigated if necessary. In this unlikely event, the following procedures will be followed as a minimum:

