7.9. Safety Stopping/ Holding Rules

Safety holding rules have been developed considering the fact that this is a first-in-human dose escalation study. Safety reviews will take place prior to each dose escalation as referenced in **Section 3.5**.

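### Section 3.1.1 runs Groups 2a and 2b in parallel with no gate, while Sections 3.1, 3.5 and 7.9 require a safety review before the higher dose, and 3.1 and 3.5 do not fix the same trigger

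*Protocol*

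**What the plan says.** Section 3.1.1 sets out which groups open after each immunogenicity review. Three branches lead to Groups 2a and 2b, and each has them running together:

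- Stage 1 target not met (3 or 4 of 6 responders): "then we proceed to Groups 2a (0.4mg) and 2b (0.8mg) in parallel".
- Poor response (2 or fewer of 6): "we proceed to Groups 2a (0.8mg) and 2b (1.2mg) in parallel".
- Expanded Group 1 falls short (9 or fewer of 12): "a further 9 participants will be recruited to group 2a (0.4) and 2b (0.8mg) each, to be run in parallel".

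None of the three mentions a safety review between 2a and 2b.

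Other sections do:

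- Section 3.1: "After review of participants in group 2a at 72hrs post dosing with the second immunisation, if no stopping criteria have been met", "then the sentinel participant at the next dose level in 2b can be vaccinated".
- Section 3.5: "After review of participants at 72hrs post dosing, if no stopping criteria have been met", the procedure may be repeated at the next dose level. The dose that starts the 72 hours is not named.
- Section 7.9: "Safety reviews will take place prior to each dose escalation", with a pointer to Section 3.5.

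Section 5.5.1 adds "Volunteers will be enrolled into each group or subgroup sequentially", in the same paragraph that says allocation is not randomised.

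**The concern.** This is a first-in-human escalation, and the sections give different answers to one operational question: when may the first person receive the higher Stage 2 dose? Section 3.1.1 is where staff would look to see what a Stage 1 result opens, and it is the section with no gate. Followed literally, it allows 2b dosing on the day 2a starts. Section 3.1 requires both 2a doses and a further 72 hours first.

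What is at stake is whether any safety information from the 2a dose exists when 2b begins. The step is largest in the poor-response branch, where 2b receives 1.2 mg and the only dose already given to anyone would be 0.2 mg, in the six people of Group 1.

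**Working it through.** The protocol states no figure for this interval, so there is nothing to reproduce. The check sets the sections side by side and then does the calendar arithmetic.

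**Inputs.** Doses on Day 0 and Day 28 (Section 3.3, Table 1). Window of ±7 days on the Day 28 visit (Section 5.2, Table 2). Review at 72 hours, i.e. 3 days (Sections 3.1 and 3.5). Group 1 has 6 people; 2a and 2b have 9 each (Table 1). Sentinel plus the next 5 participants per group (Sections 3.1 and 3.5).

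**Earliest first dose in 2b, counted from the first dose in 2a**

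| Section | Rule | Arithmetic | Day |
|---|---|---|---|
| 3.1.1 | parallel, no gate named | 0 | 0 |
| 3.5, if the first dose is meant | 72 h after dosing | 0 + 3 | 3 |
| 3.1 | 72 h after the second dose | 28 + 3 | 31 |
| 3.1, with visit window | as above | 21 + 3 to 35 + 3 | 24 to 38 |

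These days follow one participant. The one-day sentinel check would add a day to the gated rows, and a review of all of 2a would run from the last person reviewed. If 3.5 means the second dose, it agrees with 3.1. Table 2 does not settle which is meant: it has a Day 3 visit after the first dose and no visit between Day 28 and Day 42.

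Under 3.1, 2a has finished both doses before any 2b dose, so the two groups' dosing cannot overlap; only 2a's follow-up can.

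**Prior exposure if 2b starts on day 0.** In the poor-response branch, six people at 0.2 mg precede 1.2 mg, a ratio of 1.2 / 0.2 = 6. In the target-not-met branch, six people at 0.2 mg precede 0.8 mg, a ratio of 4.

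**What a gate could show (illustration only).** The chance of at least one case among n reviewed 2a participants is 1 − (1 − r)^n. The true reaction rates r are assumptions, not protocol figures. Two values of n are shown because the procedure describes a sentinel plus five (6), the group has 9, and the gate does not say how many must have been reviewed.

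| Assumed r | n = 6 | n = 9 |
|---|---|---|
| 10% | 1 − 0.9^6 = 0.47 | 1 − 0.9^9 = 0.61 |
| 20% | 1 − 0.8^6 = 0.74 | 1 − 0.8^9 = 0.87 |
| 30% | 1 − 0.7^6 = 0.88 | 1 − 0.7^9 = 0.96 |

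With same-day dosing the chance can be 0.

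**Timeline.** This is the minimum from first dose in the trial to last second dose in Stage 3, with no time for recruitment, assays or sentinel stagger. In parallel it is 56 + 56 + 28 = 140 days. With a 3-day gate it is 143, and with the 3.1 gate 140 + 31 = 171. Section 5.7 allows up to 6 months (about 182 days) for recruitment and dosing, which leaves 42, 39 and 11 days respectively.

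**The case against.** The best defence is that Section 3.1.1 concerns immunogenicity. On that view, parallel means only that one Stage 1 decision opens both groups without waiting for 2a's Week 8 titres, and the more specific safety text in 3.1 still governs when the 2b sentinel is dosed. There is one site, and it is bound by the whole protocol. Dosing 2b with no 2a data would mean setting aside 3.1, 3.5 and 7.9 together. Even then, each group has its own sentinel with a 24-hour contact, and the group holding rules in 7.9.1 apply.

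Much of this stands. Section 3.1.1 is silent on the gate; it does not cancel it. The sentinel check and holding rules do limit the exposure. Section 5.5.1 adds little, because its reference to sequential enrolment may only describe non-randomised allocation.

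What does not stand is the claim that the texts already agree. The protocol nowhere states the one-decision reading, and groups said to be run in parallel cannot be groups whose dosing must not overlap. The defence also leaves open the difference between 3.1 and 3.5 over which dose starts the 72 hours. Figure 1, which 3.1 cites for the escalation approach, is not reproduced in the text available and was not used.

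**Conclusion.** The contradiction is real and should be resolved before Stage 2 opens. Depending on the section followed, the higher Stage 2 dose may first be given on day 0, on day 3, or on about day 31 (24 to 38) after 2a's first dose. Only the gated readings guarantee any safety data from the 2a dose. The day counts rest on the protocol's own schedule; the detection probabilities rest on assumed rates and an assumed number reviewed, and are illustrative.

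A reader might infer more than the document supports:

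- That the trial has no safety gate, or has one in a single place. It does not follow: a review before escalation is required in 3.1, 3.5 and 7.9, and 3.1.1 is the section that omits it.
- That 3.1 always imposes a wait of at least a month. With the visit window the earliest day is 24.
- That the protocol must declare whether 2a against 2b is a concurrent comparison. The schedule does affect this, but Section 8.2 is mainly descriptive and says the study is not powered for precise group comparisons. It is a secondary consequence, not a separate error.

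**What to change.** Reconcile the three parallel statements in 3.1.1 with 3.1, 3.5 and 7.9 so that one release rule for the higher Stage 2 dose is stated identically in each place. The rule should say:

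- whether 2b waits for a review of 2a;
- if it does, which dose starts the 72 hours;
- which 2a participants, and how many, must have been reviewed.

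Clarify in 5.5.1 whether sequential enrolment refers to the order of allocation or to an interval between groups, and check Figure 1 against the agreed text. Which rule is kept is for the sponsor and the safety committee.

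The cost is protocol wording. If the 3.1 gate is kept, the timeline is about one month longer than under the parallel reading, and the six-month recruitment and dosing allowance should be checked against it.

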Sponsor	University Hospital Southampton NHS Foundation Trust
Trial Centres	Southampton - NIHR Clinical Research Facility, Southampton University Hospital NHS Foundation Trust, [name]
Sponsor Study Reference	RHM MED1776
Design	Open label, single-centre, first-in-human, adaptive dose escalation Phase I COVID-19 DNA vaccine trial.
Clinical Phase	
Population	Healthy, males and non-pregnant females aged 18-50 years who are immunised no less than 12 weeks prior with 2 doses of SARS-CoV-2 vaccine and have no history of serological evidence of prior SARS- CoV-2 infection (seronegative for N)
Sample size	Total: 36 volunteers
	Stage 1
	Group 1: 6 volunteers; 2 doses of pEVAC-PS at 0.2mg (lowest dose)
	Intradermally
	Stage 2 subject to safety and immunogenicity analysis from stage 1 after 4w post 2 nd dose
	Primary immunogenicity target met Expanded group 1: 12 volunteers; 2 doses of pEVAC-PS at 0.2mg intradermally
	Review for plan of reduced dose formulation and testing if continued safety and immunogenicity targets met in expanded group
	Primary immunogenicity target not met
	Group 2a: 9 volunteers; 2 doses of pEVAC-PS at 0.4mg intradermally PLUS
	Group 2b: 9 volunteers; 2 doses of pEVAC-PS at 0.8mg intradermally
	Very Poor/No response
	Group 2a: 9 volunteers; 2 doses of pEVAC-PS at 0.8mg intradermally PLUS
	Group 2b: 9 volunteers; 2 doses of pEVAC-PS at 1.2mg intradermally
	Stage 3 subject to safety and immunogenicity analysis from stage 2 after 4w post 2 nd dose

	Primary immunogenicity target met
	Group 3: 12 volunteers, 2 doses of pEVAC-PS at the dose with the
	best immunogenicity and reactogenicity profile from Groups 2a or 2b
	Primary immunogenicity target not met at 2x 0.8mg ID
	Group 2c: 12 volunteers; 2 doses of pEVAC-PS at 1.2mg intradermally
Follow up	COVID-19 vaccinated volunteers (immunised no less than 12 weeks
duration	prior to enrolment), and who have no prior history or serological
	evidence of SARS-CoV-2 infection will be followed up for a total of
	approximately 6 months from the time of receiving the first dose of
	pEVAC-PS (this is an estimate and may vary in accordance with the
	specified time windows for each attendance).
Planned Trial	18 months (this includes up to 6 months during the recruitment and
Period	dosing phase with a follow-up period of up to 12 months).
Primary Objective	To assess the safety and reactogenicity of a new pan-Sarbeco
	Coronavirus DNA candidate vaccine pEVAC-PS in a boosting regime

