2 additional groups consisting of 9 participants will be enrolled. Group 2a will receive 2 administrations of 0.8mg ID, and group 2b will receive 2 administrations of 1.2mg ID.

There will be a review conducted of the safety and immunogenicity data 4 weeks after the second administration of vaccine for groups 2a and 2b to determine how to proceed in Stage 3.

Stage 3

If primary immunogenicity target is met during stage 2, then the group with the optimum immunogenicity and reactogenicity profile from Groups 2a or 2b will be expanded with an additional 12 participants in Group 3.

If the target is not met from group 2a or 2b (0.8mg), then an additional 12 participants will be enrolled into group 2c, who will receive 2 administrations of 1.2mg ID.

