3.5.1. Rationale and Design of Dose optimisation Strategy

Current formulation constraints mean that the minimum dose of pEVAC-PS which can be administered intradermally is 0.2mg, and the maximum is 1.2mg. An adaptive protocol allows optimisation within this dosing range with potential to expand groups which achieve desirable immunogenicity and reactogenicity profiles.

Sufficient immune responses are expected from significantly lower doses administered intradermally given the increased numbers of antigen presenting cells present within the dermis as compared to muscle cells.

The adaptive design from intradermal administration starts at the lowest currently achievable dose. If that is successful, this dosing group will be expanded, and the team will review the potential for additional groups receiving lower doses (this will require adaptation of the formulation).

If primary immunogenicity endpoints are not met, successive groups will be enrolled at higher doses until the pre specified immunogenicity target is met. At this point, the group with the optimum immunogenicity and reactogenicity profile will be further expanded.

4. Participant Eligibility Criteria

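### In the 0.4/0.8 mg branch, the escalation rule in 3.1.1 literally fires on a split result that is meant to lead to expansion; at 10–11 of 12 on 0.2 mg, 3.1 and 3.1.1 prescribe different actions

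*Protocol*

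**What the plan says.** Section 3.1.1 makes the responder count in each group the basis for choosing the next dose.

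**Branch after 3–4 of 6 at 0.2 mg.** Groups 2a (0.4 mg) and 2b (0.8 mg) enrol 9 each. Two rules follow:
- Expansion: "if 7-9 or more participants have a 2-fold increase in Ab titre (at 0.4 or 0.8 mg) we expand whichever group" has more responders.
- Escalation: "if <7 participants have a 2-fold increase in Ab titre (at 0.4 or 0.8 mg) we move to Stage 3 and increase dose", the new dose being 1.2 mg.

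**Other places that bear on this choice:**
- Section 3.1.1, branch after 2 or fewer of 6: "if <7 participants have a 2-fold increase in Ab titre at 0.8mg and 1.2mg the trial will conclude".
- Section 3.1 (Stage 3), repeated in Table 1: "If the target is not met from group 2a or 2b (0.8mg"), then 12 volunteers enter Group 2c at 1.2 mg.
- Synopsis, Stage 3 heading above Group 2c: "Primary immunogenicity target not met at 2x 0.8mg ID".
- Section 3.5.1: dose levels rise "until the pre specified immunogenicity target is met. At this point, the group with the optimum immunogenicity and reactogenicity profile will be further expanded".
- Section 3.1, cap: "This study will recruit up to 36 healthy volunteers in up to 3 stages".

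**Expanded Group 1 (0.2 mg, 12 volunteers).** Section 3.1.1 says "if 10 or more of the 12 participants have at least a 2-fold increase in Ab titre (at 0.2mg) we select 0.2mg" for Phase II. At 12 of 12 it says that re-formulation to a lower dose may be considered for a new study, and at 9 or fewer it opens 0.4 mg and 0.8 mg. Section 3.1 says that if safety is acceptable and the targets are still met, the study halts and a reduced-dose formulation follows by amendment. The Synopsis likewise goes to a reduced-dose review.

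**The concern.** The two Stage 2 rules should divide the possible results between them. Because both carry the same *or*, they overlap whenever exactly one group reaches 7 of 9. The literal text then calls for expanding the successful group and also for moving to 1.2 mg.

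The choice decides whether the last 12 healthy volunteers receive the highest dose of a first-in-human trial or a lower dose that already met its target. It also decides whether the final dose has 21 participants, as section 8.1 intends for Group 3, or 12.

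For Expanded Group 1 the number exposed does not change, but the trial's conclusion does: take 0.2 mg to Phase II, or stop and look for something lower.

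**Working it through.** **1. Reproduce the plan's totals.**
- Stage 1 + 2a + 2b + one Stage 3 cohort: 6 + 9 + 9 + 12 = 36.
- Expanded Group 1 followed by 2a and 2b: 6 + 12 + 9 + 9 = 36.
- Participants at the dose carried into Group 3: 9 + 12 = 21.

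The stated 36 and 21 are both reproduced. Carrying out both Stage 3 actions would need 6 + 9 + 9 + 12 + 12 = 48, above the cap.

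**2. Count the overlap.** Each group can have 0 to 9 responders, giving 10 × 10 = 100 result pairs. Three counts meet target (7, 8, 9) and seven do not (0 to 6). Pairs with exactly one group meeting target: 2 × 3 × 7 = 42. All 42 satisfy both rules as written. If escalation required failure at both doses, the number would be 0.

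**3. How likely is a split?** The protocol states no response rates, so those below are assumptions. Everything is conditional on entering the 3–4 of 6 branch.

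P(at least 7 of 9), binomial: 0.2318 at a true rate of 0.6; 0.4628 at 0.7; 0.7382 at 0.8; 0.9470 at 0.9.

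Let A be this probability at 0.4 mg and B at 0.8 mg. Only 0.4 mg meets target: A(1 − B). Only 0.8 mg meets target: B(1 − A).

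| True rates 0.4/0.8 mg | Only 0.4 mg meets | Only 0.8 mg meets | Any split |
|---|---|---|---|
| 0.6/0.8 | 0.2318 × 0.2618 = 0.061 | 0.7382 × 0.7682 = 0.567 | 0.628 |
| 0.7/0.8 | 0.4628 × 0.2618 = 0.121 | 0.7382 × 0.5372 = 0.397 | 0.518 |
| 0.8/0.9 | 0.7382 × 0.0530 = 0.039 | 0.9470 × 0.2618 = 0.248 | 0.287 |
| 0.7/0.7 | 0.4628 × 0.5372 = 0.249 | 0.249 | 0.497 |

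The two kinds of split differ in what the text says. If only 0.8 mg meets target, the Synopsis points to Group 3 and the pull towards 1.2 mg comes from the *or* in 3.1.1. If only 0.4 mg meets target, the Synopsis heading for 1.2 mg is satisfied as well. That second column, 4–12% under a rising dose-response and 25% at 0.7/0.7, is the sharper conflict.

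**4. Expanded Group 1.** The Stage 1 target is 5/6 = 83.3%, and 10/12 = 83.3%. Section 3.1.1 treats 9 or fewer as failure, so 10 or 11 of 12 is naturally read as the target still being met. With that reading:

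| Result | 3.1.1 | 3.1 | Synopsis |
|---|---|---|---|
| 10–11 of 12 | 0.2 mg to Phase II | halt, reduced-dose formulation by amendment | reduced-dose review |
| 12 of 12 | consider re-formulation | as above | as above |

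P(10 or 11 of 12) = 66p¹⁰(1 − p)² + 12p¹¹(1 − p). This is 0.490, 0.607 and 0.440 at true rates of 0.80, 0.90 and 0.95, given that the group opens.

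**The case against.** The strongest reply is that the intent is clear. Section 3.5.1 gives an order: escalate until the target is met, then expand. In ordinary English, a target not met from 2a or 2b is met from neither, so 3.1 and Table 1 already say the sensible thing. The expansion bullet handles a split, because the group with at least 7 responders necessarily has the higher count. The *and* in the parallel branch points the same way, and the cap of 36 makes doing both unworkable. Section 8.1 also leaves adaptation decisions to the investigators on all available information.

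Most of this stands. A reader might infer that the protocol gives no indication of which action prevails, or that 3.1 and Table 1 repeat the contradiction. The documents do not support either. A reader might also take the split probabilities of up to 63% as the chance of a wrong action. They are not: in the rising scenarios most of that is 0.8 mg meeting target, where the Synopsis agrees with expansion. The sharper case is smaller still before Stage 1 is known. With assumed 0.2 mg rates of 0.7 and 0.6, the chance of 3–4 of 6 is 0.509 and 0.588, giving 0.039 × 0.509 = 2% to 0.121 × 0.588 = 7% in the rising scenarios.

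What the reply does not remove is the escalation bullet, which sits in the section holding the operative counts and says the opposite of the intent, and the Synopsis heading, which looks at 0.8 mg alone. General discretion in 8.1 does not reconcile two prespecified triggers, and section 11.4 bars planned deviations, so it matters which action complies.

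On Expanded Group 1, choosing 0.2 mg and reviewing a lower formulation could coexist, and 3.5.1 mentions such a review. But 3.1 halts the study to plan a reduced dose, whereas 3.1.1 raises dose reduction only at 12 of 12. Figure 1 could not be checked; it may show the intended order, but it would not change these sentences.

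**Conclusion.** The concern holds in limited form: the rule is wrong as written, and the intended rule can be recovered from the rest of the protocol.

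(a) The escalation bullet in the 3–4 of 6 branch of 3.1.1 contradicts the intended action on a split result. The Synopsis heading additionally opens 1.2 mg when 0.4 mg succeeded and 0.8 mg did not: about 4–12% with a rising dose-response and 25% at 0.7/0.7, on assumed rates and given entry to the branch.

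(b) At 10–11 of 12 in Expanded Group 1, 3.1.1 differs from 3.1 and the Synopsis. This rests on reading 10 of 12 as target met. At 12 of 12 a reader might see the same clash, but 3.1.1 only asks for re-formulation to be considered there, so no conflict is claimed.

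No error rate or power statement is affected. The point is worth correcting because it bears on which dose the last 12 volunteers receive and on what the trial recommends.

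**What to change.** - **3.1.1, branch after 3–4 of 6:** escalate to 1.2 mg (Group 2c) only if fewer than 7 of 9 respond at both 0.4 mg and 0.8 mg; otherwise expand a group with at least 7 of 9.
- **Synopsis:** replace the trigger on 0.8 mg alone with the same condition.
- **3.1 and Table 1:** for clarity, say that neither group met the target.
- **Expanded Group 1, in 3.1 and the Synopsis:** follow 3.1.1, with 10–11 of 12 selecting 0.2 mg and 12 of 12 leading to consideration of re-formulation.

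The cost is amendment text only. No participants, visits or assays are added, and the maximum stays at 36.
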